5 SUBJECT POPULATIONS (ANALYSIS SETS)

5.1 Efficacy

5.1.1 Full analysis set (FAS)

In accordance with the Intention To Treat (ITT) principle, the FAS population includes all subjects who received the study drug and completed the ^{99m}Tc-rhAnnexin V-128 imaging procedure.

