5.3 Primary population

The primary and secondary efficacy analysis will be based on the FAS population.

The primary efficacy analysis on the Primary endpoint of Phase II will be also performed on the PP population as supportive analysis.

The assessment of safety and tolerability will be based on the Safety population.

Version: 01 Page: **24 of 167**

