6.1.13 Rules and data formats

Data will be presented using an appropriate number of decimal places (i.e. the number of decimal places used does not imply undue precision). Raw data will be presented to the number of decimal places collected, and derived data will be presented to an appropriate number of decimal places. The appropriate number of decimal places will be determined by general practice, mathematical rationale or scientific rationale (e.g. age should be presented in whole numbers).

For summary statistics, the following will be presented: number of non-missing values (n), number of missing values, arithmetic mean, standard deviation, median, the IQR (first quartile, third quartile), the range (minimum, maximum) and, only if appropriate, 95% 2-sided confidence interval.

Mean, standard deviation, first quartile, median, third quartile and confidence interval values will be rounded to one more decimal place than the raw data whereas minimum and maximum will be reported with the same precision as the raw data.

Percentages will be reported to one decimal place. Percentages will be calculated using a denominator of all subjects in a specified population. The denominator will be specified in a footnote to the tables for clarification if necessary.

p-values will be reported to four decimal places (e.g., p=0.0037), after rounding; p-values which are less than 0.0001 will be presented as "<0.0001".

Version: 01 Page: **31 of 167**

All text fields must be left justified and numeric or numeric with some text specification (e.g., not done, unknown, <4.5, ...) must be decimal justified. Dates will be presented in the format [dd/mm/yyyy] and times in the format [hh:mm] using 24-hour clock scale.

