* Patient = Subject with asymptomatic plaque; Control = Healthy volunteer

Confidential

Version: 01 Page: **52 of 167**

Listing 16.2.4.4/1: Prior and Concomitant Medications

		Medication	ATC description						
Subject ID	Subject group*	trade name	(third level)	Enrollment date	Start date	Partial date	Ongoing?	End date	Partial date
PAT_PATNUMBER	PAT_INFCONS_TYPE	CM_NAME	ATC_LV3_DESC R	PAT_FIRSTVISITDAT E	CM_START_DATE	CM_PARTIAL_STAR T_DATE	CM_ONGOING_YN	CM_END_DATE	CM_PARTIAL_END_ DATE
04-CA-001	Patient	XXXXXXX	XXXXXX	11/03/2011	15/08/1990	Day	No	14/04/1994	
04-CA-002	Control	XXXXXXX	XXXXXX	09/04/2011	31/12/2007		No	15/06/2008	Day&Month
04-CA-003	Control	XXXXXXX	XXXXXX	10/07/2011	05/05/2005		Yes		

Data Source Table: W_PATIENT, W_CM.

Dictionary Name: ATC Drug Dictionary Version: 2016

Note: NA = Not Available

* Patient = Subject with asymptomatic plaque; Control = Healthy volunteer

Version: 01 Page: **53 of 167**

Listing 16.2.4.4/2: Prior and Concomitant Medications

		Medication	ATC description				Frequency of	Specify other	Route of	
Subject ID	Subject group*	trade name	(third level)	Total daily dose	Unit	Specify other unit	administration	frequency	administration	Specify other route
PAT_PATNUMBE R	PAT_INFCONS_T YPE	CM_NAME	ATC_LV3_DESCR	CM_DOSE	CM_DOSEU	CM_DOSEU_SP	CM_FREQ	CM_FREQ_SP	CM_ROUTE	CM_ROUTE_SP
04-CA-001	Patient	XXXXXXX	XXXXXX	3	G		BID		Otherl	XXXXXX
04-CA-002	Control	XXXXXXX	XXXXXX	3	Other	XXXXXX	TID		Intramuscolar	
04-CA-003	Control	XXXXXXX	XXXXXX	12	Mg		Other	XXXXXX	Subcutaneous	

Data Source Table: W_PATIENT, W_CM.

Dictionary Name: ATC Drug Dictionary Version: 2016

Note: NA = Not Available

* Patient = Subject with asymptomatic plaque; Control = Healthy volunteer

Confidential

Version: 01 Page: **54 of 167**

Listing 16.2.5.1/1: Study Drug Administration and Extent of Subject Exposure

-	Subject ID	Subject group*	Has the injection been performed?	Reason for not performing the injection	Injection date	Injection time	Batch of kit	Batch of ^{99m} Tc generator	_
	PAT_PATNUMBER	PAT_INFCONS_TYPE	ANN_YN	ANN_YN_SP	ANN_DATE	ANN_TIME	ANN_KIT	ANN_GEN	
	04-CA-001	Patient	Yes		11/03/2011	10:50	09101-110631	09101-110631	
	04-CA-002	Control	Yes		03/03/2011	10:00	09101-110981	09101-110981	
	04-CA-003	Control	No	XXXXXXX					

Data Source Table: W_PATIENT, W_ANN.

Note: NA = Not Available

* Patient = Subject with asymptomatic plaque; Control = Healthy volunteer

Confidential

Version: 01 Page: **55 of 167**

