11.2 Standard Tables

Version: 01 Page: **79 of 167**

 Table 14.1.1:
 Subject Disposition

POPULATION	STATISTIC	PATIENT* (N=xx)	CONTROL* (N=xx)	ALL SUBJECTS (N=xx)
Screened subjects	n (%)	99 (99.9)	99 (99.9)	99 (99.9)
Screen failures	n (%)	99 (99.9)	99 (99.9)	99 (99.9)
Reason 1	n (%)	99 (99.9)	99 (99.9)	99 (99.9)
	n (%)	99 (99.9)	99 (99.9)	99 (99.9)
Reason m	n (%)	99 (99.9)	99 (99.9)	99 (99.9)
Enrolled subjects	n (%)	99 (99.9)	99 (99.9)	99 (99.9)
Dosed subjects	n (%)	99 (99.9)	99 (99.9)	99 (99.9)
Completed study subjects	n (%)	99 (99.9)	99 (99.9)	99 (99.9)
Discontinued study subjects	n (%)	99 (99.9)	99 (99.9)	99 (99.9)
Reason 1	n (%)	99 (99.9)	99 (99.9)	99 (99.9)
	n (%)	99 (99.9)	99 (99.9)	99 (99.9)
Reason m	n (%)	99 (99.9)	99 (99.9)	99 (99.9)

Source: Data listings {Specify data listing number(s)} Analysis dataset: {Specify datasets}

Note: All percentages are based upon the number of screened subjects.

^{*} Patient = Subject with asymptomatic plaque; Control = Healthy volunteer

Statistical Analysis Plan ANNEXIN 04

Confidential

Version: 01 Page: **80 of 167**

 Table 14.1.2:
 Analysis Populations

ANALYSIS SET	STATISTIC	PATIENT* (N=xx)	CONTROL* (N=xx)	ALL SUBJECTS (N=xx)
Full Analysis Set (FAS)	n (%)	99 (99.9)	99 (99.9)	99 (99.9)
Per Protocol population (PP)	n (%)	99 (99.9)	99 (99.9)	99 (99.9)
Safety population	n (%)	99 (99.9)	99 (99.9)	99 (99.9)

Source: Data listings {Specify data listing number(s)} Analysis dataset: {Specify datasets}

Note: All percentages are based upon the number of screened subjects.

^{*} Patient = Subject with asymptomatic plaque; Control = Healthy volunteer

Version: 01 Page: **81 of 167**

Table 14.1.3: Protocol Deviations

PROTOCOL DEVIATION	STATISTIC	PATIENT* (N=xx)	CONTROL* (N=xx)	ALL SUBJECTS (N=xx)
Subjects with any minor protocol deviations	n (%)	99 (99.9)	99 (99.9)	99 (99.9)
Minor deviation 1	n (%)	99 (99.9)	99 (99.9)	99 (99.9)
	n (%)	99 (99.9)	99 (99.9)	99 (99.9)
Minor deviation m	n (%)	99 (99.9)	99 (99.9)	99 (99.9)
Subjects with any major protocol deviations	n (%)	99 (99.9)	99 (99.9)	99 (99.9)
Major deviation 1	n (%)	99 (99.9)	99 (99.9)	99 (99.9)
	n (%)	99 (99.9)	99 (99.9)	99 (99.9)
Major deviation m	n (%)	99 (99.9)	99 (99.9)	99 (99.9)

Source: Data listings {Specify data listing number(s)} Analysis dataset: {Specify datasets}

Note: All percentages are based upon the number of screened subjects.

^{*} Patient = Subject with asymptomatic plaque; Control = Healthy volunteer

Version: 01 Page: **82 of 167**

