^{*} Patient = Subject with asymptomatic plaque; Control = Healthy volunteer

Version: 01 Page: **90 of 167**

Table 14.1.8.1/3: Study Drug Administration – Safety Population

QUALITY CONTROL ON THE FINAL PRODUCT	STATISTIC	PATIENT* (N=xx)	CONTROL* (N=xx)
Actual dose injected (MBq)	n	99	99
	Missing	99	99
	Mean	99.9	99.9
	S.D.	99.9	99.9
	Median	99.9	99.9
	Q1, Q3	99.9, 99.9	99.9, 99.9
	Min, Max	99, 99	99, 99
Volume of administered solution (mL)	n	99	99
, ,	Missing	99	99
	Mean	99.9	99.9
	S.D.	99.9	99.9
	Median	99.9	99.9
	Q1, Q3	99.9, 99.9	99.9, 99.9
	Min, Max	99, 99	99, 99

Source: Data listings {Specify data listing number(s)} Analysis dataset: {Specify datasets}

^{*} Patient = Subject with asymptomatic plaque; Control = Healthy volunteer

Version: 01 Page: **91 of 167**

Table 14.2.1.1: Carotid and Aorta Imaging Assessment – Prevalence of Positive Scans – FAS Population

TIME POINT		STATISTIC	PATIENT* (N=xx)	CONTROL* (N=xx)
60 mins after IP injection	Positive	n (%)	99 (99.9)	99 (99.9)
		95% C.I.	99.9 - 99.9	99.9 - 99.9
	Negative	n (%)	99 (99.9)	99 (99.9)
	Missing	n (%)	99 (99.9)	99 (99.9)
120 mins after IP injection	Positive	n (%)	99 (99.9)	99 (99.9)
		95% C.I.	99.9 - 99.9	99.9 - 99.9
	Negative	n (%)	99 (99.9)	99 (99.9)
	Missing	n (%)	99 (99.9)	99 (99.9)
Overall#	Positive	n (%)	99 (99.9)	99 (99.9)
		95% C.I.	99.9 - 99.9	99.9 - 99.9
	Negative	n (%)	99 (99.9)	99 (99.9)
	Missing	n (%)	99 (99.9)	99 (99.9)

Source: Data listings {Specify data listing number(s)} Analysis dataset: {Specify datasets}

Notes: All percentages are based upon the number of enrolled subjects by group.

Confidence intervals are estimated using the exact (Clopper-Pearson) formula for binomial proportions.

^{*} Patient = Subject with asymptomatic plaque; Control = Healthy volunteer

[#] Subjects with either a positive scan at 60 or 120 minutes post injection will be considered overall positive

Version: 01 Page: **92 of 167**

Table 14.2.1.2: Carotid and Aorta Imaging Assessment – Prevalence of Positive Scans – PP Population

IMAGING PROCEDURE		STATISTIC	PATIENT* (N=xx)	CONTROL* (N=xx)
SPECT (60 mins after IP injection)	Positive	n (%)	99 (99.9)	99 (99.9)
		95% C.I.	99.9 - 99.9	99.9 - 99.9
	Negative	n (%)	99 (99.9)	99 (99.9)
	Missing	n (%)	99 (99.9)	99 (99.9)
SPECT/CT (120 mins after IP injection)	Positive	n (%)	99 (99.9)	99 (99.9)
		95% C.I.	99.9 - 99.9	99.9 - 99.9
	Negative	n (%)	99 (99.9)	99 (99.9)
	Missing	n (%)	99 (99.9)	99 (99.9)
Overall#	Positive	n (%)	99 (99.9)	99 (99.9)

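### The primary prevalence and adverse-event table shells divide by enrolled subjects, not by the FAS, PP or Safety set in their titles

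*SAP*

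**What the plan says.** SAP 5.3 names the populations. For efficacy, "The primary and secondary efficacy analysis will be based on the FAS population", with the PP set as support for the Phase II primary endpoint. For safety, "The assessment of safety and tolerability will be based on the Safety population". SAP 5.1.1 makes the FAS conditional on dosing and on imaging: "the FAS population includes all subjects who received the study drug and completed the" imaging procedure. The PP set is the FAS without major deviations, and the Safety set is everyone dosed. Section 5 defines no other set.

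On denominators, SAP 6.1.13 says "Percentages will be calculated using a denominator of all subjects in a specified population", and then "The denominator will be specified in a footnote to the tables for clarification if necessary".

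The shells in SAP 11.2 say something else. Tables 14.2.1.1 (FAS), 14.2.1.2 (PP) and 14.3.1.2 to 14.3.1.7 (Safety) all note that "All percentages are based upon the number of enrolled subjects by group". The same note is on the demographics, carotid ultrasound, medical-history and medication shells (14.1.4.1, 14.1.5.1, 14.1.6.1, 14.1.7.1 and 14.1.7.2). Tables 14.2.1.3 and 14.3.1.1 do not carry it.

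**The concern.** The Phase II primary endpoint is a single proportion, so its denominator is half of the result. The title and SAP 5.3 point to one denominator and the footnote to another. A programmer would have good reason to follow the footnote: SAP 6.1.13 makes footnotes the place where a denominator is stated, and SAP section 10 gives the denominator of a percentage as an example of what they should clarify.

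A subject who is enrolled but outside the titled set cannot add to the numerator but would still count in the denominator. Prevalence and adverse-event rates can therefore only be pulled down. The FAS and PP tables would also share one denominator. As the PP set is contained in the FAS, the printed PP prevalence could never exceed the printed FAS prevalence, whatever the data showed. The supportive analysis could then seem to disagree with the primary one only because subjects had been excluded.

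The shells name the exact Clopper-Pearson method but not its n. The interval either uses the wrong denominator too or does not match the percentage printed above it.

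**Working it through.** **Can the counts differ?** The plan allows for it.
- Table 14.1.1 gives enrolled subjects and "Dosed subjects" separate rows.
- The protocol's visit schedule repeats the eligibility check and the pregnancy test on Day 0, so a participant can be lost between enrolment and injection.
- SAP 6.1.7 provides for a Safety population that differs from the FAS.
- Listing 16.2.5.1/1 has a field headed "Reason for not performing the injection".
- Protocol 12.1 computes precision for 30 patients and recruits 35 to allow for attrition.

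**Formula.** With x positive subjects in the titled set, the correct percentage is x/N_set and the printed one is x/N_enrolled. Hence

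printed = correct × (N_set / N_enrolled).

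The exact 95% limits for x out of n are the 0.025 quantile of Beta(x, n − x + 1) and the 0.975 quantile of Beta(x + 1, n − x).

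**Inputs.** The planned 35 patients and 10 controls come from Protocol 12.1 and SAP 4.3.5. The anticipated prevalence of 0.3 to 0.5 comes from Protocol 5.1. The plan gives no set sizes and no prevalence result to reproduce, so every set size and numerator below is an assumption. The printed column applies the enrolled n to the interval as well.

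| Assumed set | Factor | Correct | Printed as written |
|---|---|---|---|
| FAS 35 of 35 | 35/35 = 1.000 | no change | no change |
| FAS 34 of 35 | 34/35 = 0.971 | 15/34 = 44.1% (27.2–62.1) | 15/35 = 42.9% (26.3–60.6) |
| FAS 33 of 35 | 33/35 = 0.943 | 9/33 = 27.3% (13.3–45.5) | 9/35 = 25.7% (12.5–43.3) |
| FAS 30 of 35 | 30/35 = 0.857 | 9/30 = 30.0% (14.7–49.4) | 9/35 = 25.7% (12.5–43.3) |
| FAS 30 of 35 | 30/35 = 0.857 | 15/30 = 50.0% (31.3–68.7) | 15/35 = 42.9% (26.3–60.6) |
| PP 28 of 35 | 28/35 = 0.800 | 14/28 = 50.0% (30.6–69.4) | 14/35 = 40.0% (23.9–57.9) |
| Controls, 9 of 10 | 9/10 = 0.900 | 1/9 = 11.1% (0.3–48.2) | 1/10 = 10.0% (0.3–44.5) |
| Safety 33 of 35 | 33/35 = 0.943 | 3/33 = 9.1% | 3/35 = 8.6% |

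**What enrolled means.** Table 14.1.1 separates screened from enrolled subjects, but Protocol 15.4 describes enrolled participants as everyone who consented to screening. On that wider reading screening failures enter the denominator. If 40 patients consented and 30 were in the FAS, the factor is 30/40 = 0.750: 9/30 = 30.0% would print as 9/40 = 22.5% (10.8–38.5), and 15/30 = 50.0% as 15/40 = 37.5% (22.7–54.2).

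**The case against.** The best defence is that this is footnote wording with little practical effect. SAP 5.3 names the primary population clearly. The shells print counts and a column N, so a reader can recompute. The protocol calls the efficacy analysis mainly descriptive, no success threshold for prevalence is stated, and SAP 7.3 requires an independent check of subject numbers and of consistency with the plan. SAP 6.1.13 speaks of a specified population, not the titled one, and lets a footnote state the denominator. Imaging follows a single injection by one and two hours at the same visit, so few dosed patients should be lost before the FAS. The synopsis plans 35 evaluable patients, so 30 of 35 is not the expected case. The listing field for an injection not given is weak evidence, because listings cover all screened subjects and such a row may be a screening failure.

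Much of this limits the size. Losses may be small: at 34 of 35 the shift is 44.1% to 42.9%, against an exact interval 34.9 points wide (62.1 − 27.2). The listing field alone does not show that enrolled and dosed counts will differ; the separate rows in Table 14.1.1 and the Day 0 re-check are better evidence. For the adverse-event tables, an enrolled but undosed subject is needed.

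None of it removes the conflict. A specified population most naturally means one of the section 5 sets, and leave to state a denominator for clarification is not leave to replace the titled set with an undefined one. Printed counts do not correct a wrong headline percentage or interval. A check against the plan cannot settle the matter when the plan gives two answers.

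**Conclusion.** The concern holds. As written, the shells give a wrong primary percentage and wrong adverse-event percentages whenever an enrolled subject is outside the titled set. The error always lowers the rate, by the factor N_set/N_enrolled. On the illustrative set sizes with 35 enrolled patients, that runs from no change (35 of 35) through 0.971 (34 of 35) to 0.857 (30 of 35) for the FAS, and 0.800 for a PP set of 28. At 30 of 35, a prevalence of 30.0%, the bottom of the hypothesised range, would print as 25.7%, below that range. The direction and the formula follow from the text; the sizes rest on assumed counts. Reading enrolled as in Protocol 15.4 could only make the effect larger. This should be corrected before the tables are produced, so that the primary denominator is not chosen after results are seen.

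**What to change.** In Tables 14.2.1.1, 14.2.1.2, 14.3.1.2 to 14.3.1.7 and the other FAS and Safety shells with this note, replace it with: *Percentages are based on the number of subjects in the titled population (FAS, PP or Safety) in each group.* In Tables 14.2.1.1 and 14.2.1.2 add: *The Clopper-Pearson interval uses the same n as the printed percentage.* Define enrolled once, for Table 14.1.1, and reconcile that definition with Protocol 15.4.

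The cost is a set of footnote edits and the matching denominators in the table programs; no new data are needed. One consequence should be accepted knowingly: a FAS subject with a missing scan stays in the denominator and so counts as not positive in both the percentage and the interval. SAP 6.1.13 already implies this, and the shells' row for missing results makes it visible.

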11.3 Standard Figures

The different lines on the figures should look different (e.g. dotted lines) rather than using different colours so that the lines can be distinguished when using a non-colour printer.

Version: 01 Page: **156 of 167**

[figure not shown]
Figure 14.2.1.1: Left Carotid Target to Background Ratio (TBR) Imaging
Assessment - Patients - Carotid with Stenosis ≥ 50% - FAS
Population - 60 mins after IP injection

[figure not shown]
Version: 01 Page: **157 of 167**

[figure not shown]

[figure not shown]
Version: 01 Page: **158 of 167**

[figure not shown]

[figure not shown]
Version: 01 Page: **159 of 167**

[figure not shown]

[figure not shown]
Version: 01 Page: **160 of 167**

[figure not shown]

[figure not shown]
Version: 01 Page: **161 of 167**

[figure not shown]

[figure not shown]
Version: 01 Page: **162 of 167**

[figure not shown]

Version: 01 Page: **163 of 167**

[figure not shown]

Version: 01 Page: **164 of 167**

[figure not shown]

Version: 01 Page: **165 of 167**

Statistical Analysis Plan ANNEXIN 04

Version: 01 Page: **166 of 167**

12 APPENDICES TO THE SAP TEMPLATE

12.1 Derived data

The following derived data will be calculated and included in the listings or in the tables:

(1) Age

Subject age (years) will be derived as (informed conset date - birth date)/365.25 and truncated to the largest integer that is less than or equal to the calculated result. Since birth date is truncated (i.e. only month and year will be filled in the eCRF), it will be approximated using "01" as value for the day.

(2) **BMI**

BMI (kg/m²) will be automatically derived as [weight] (kg)/([height](cm)/100)² and rounded to the nearest decimal.

(3) Time from injection

Time from injection (min) will be derived as the difference between SPECT/CT scan time [SP_TIME/SPCT_TIME] and injection time [ANN_TIME].

(4) Adverse event duration

If the start and end dates of the adverse event are identical then "<1" day will be presented with the duration in hh:mm recorded in the eCRF if it is available. If times are available, the duration will be calculated as (end date/time - start date/time) and presented in days hh:mm. If at least one time is missing and if the duration is greater than 24 hours then it will be calculated as (end date - start date)+1 and presented in days. If the recorded end date is CONT. (for continuing), the end date will be listed as "ongoing" and the duration will be approximated as "≥(last attended visit date - start date)+1" day(s). If the start date or the end date are partial the duration will be presented as a superior inequality "≥ xx" day(s) (i.e. "≥2" where start date = 31JAN2004 and end date = FEB2004 or start date = JAN2004 and end date = 01FEB2004).

(5) Study day of onset

If the start date of the adverse event is identical to the date of injection, then "1" day will be presented with the time to onset in hh:mm recorded in the eCRF if it is available. If the date of onset is greater than the date of injection then it will be calculated as (start date - injection date+1) and presented in days. If the date of onset precedes the date of injection the study day will be calculated as (start date - injection date). If the start date is partial, the time since injection will be presented as a superior

Statistical Analysis Plan ANNEXIN 04

Confidential

Version: 01 Page: **167 of 167**

inequality (i.e. for an AE started in FEB2004 after the injection performed on 31JAN2004, the delay of onset will be "≥2" days).

12.2 SAS programs

This section provides the SAS programs related to the statistical tests specified in the statistical methods section 6. All computer output from SAS statistical programs used as a basis for extracted results should be retained for review by Responsible of statistical analysis.

4			
7	1 1212	manır	NUITATION
	Dala	HIAHIL	ulation

Proc Format

Proc Print

Proc Sort

Proc SQL

Proc Transpose

2 Descriptive statistics

Proc Corr

Proc Freq

Proc Means

Proc Tabulate

3 Test statistics

Proc Ttest

4 Graphs

Proc Boxplot

Proc Sgplot
